### 3. Abstract:

Above-the-knee amputations are associated with a high mortality rate, ranging from 2.8-35% postoperatively [1, 2]. The role of anesthetic choice in these patients, particularly with regards to mortality, is unknown. Patients undergoing these procedures are typically elderly and fraught with medical comorbidities which commonly include peripheral vascular disease, diabetes, hypertension, coronary artery disease, and COPD [1-3].

Peripheral nerve blocks have been beneficial in the treatment of postoperative pain after lower extremity amputation, resulting in lower pain scores and analgesia consumption [3, 4]. There are case reports and small case series (the largest containing 10 patients) detailing the use of peripheral nerve blocks as a primary anesthetic in this high-risk patient population [5-8]. The benefits reported include avoidance of intubation, mechanical ventilation, and the hemodynamic swings associated with general anesthesia as well as excellent pain control postoperatively.

To the best of my knowledge and search of the existing literature, peripheral nerve blocks have not been evaluated prospectively as a primary anesthetic in the setting of above-the-knee amputations. The results of this study may assist clinicians in choosing the appropriate anesthetic option for Veterans undergoing this type of surgery. The purpose of this pilot study would be to determine the feasibility of lower extremity nerve blocks and sedation for above-the-knee amputations. The results of this investigation may be used to guide future studies regarding the optimal anesthetic technique(s) for major lower extremity amputation.

#### 4. Background:

Avoidance of general anesthesia in this high-risk patient population may have additional benefits beyond improved postoperative pain scores and analgesic consumption. The current literature is limited when evaluating anesthetic type for major lower extremity amputation and typically categorize patients as having received general or regional anesthesia. A major shortcoming of the current literature, however, is the inclusion of neuraxial anesthesia, peripheral nerve blocks, or a combination thereof in the regional anesthesia category [1, 2].

[figure not shown]
According to the latest report from the VA National Surgery Office, an above-the-knee amputation has a 5.6% 30-day mortality rate. It is unknown if these blocks can be utilized consistently as a primary anesthetic or if their use may result in a decreased 30-day mortality.

#### 5. Specific Aims:

The primary objective will be to evaluate the ability of the femoral, sciatic, lateral femoral cutaneous nerve (LFCN), and obturator blocks to provide surgical anesthesia. Surgical anesthesia will be defined as the performance of surgery using only sedative medications (propofol or dexmedetomidine) without the need for opioids/analgesic agents, local anesthetic infiltration, or conversion to general anesthesia. These four nerves are the primary innervation to the skin and musculoskeletal structures of the leg.

Instances of intraoperative analgesic administration or conversion to general anesthesia will be compared.

Secondary objectives will include assessments of block performance times, block onset characteristics defined by onset of decreased sensorimotor function in nerve distribution of the blocked extremity, postoperative pain scores (using a numerical rating scale) and analgesic administration, PACU discharge times, patient satisfaction, and 30-day mortality rate. Adverse events related to the anesthetic and surgical techniques will also be recorded.

## **6. Research Plan:**

Veterans scheduled for above-the-knee amputation or knee disarticulation will be invited to participate in the study. Peripheral nerve blocks as well as general anesthesia are commonly employed anesthetic techniques for these surgical procedures.

### Inclusion criteria

1. Patients  $\geq 18$  years of age undergoing above-the-knee amputation or knee disarticulation
2. Ability to understand and provide informed consent

### Exclusion criteria

1. Patient refusal or inability to provide informed consent
2. True allergy, not sensitivity, to any of the following substances:
  - a. Local anesthetics
  - b. Propofol or other sedative agents
  - c. General anesthetic agents
3. Pregnancy
4. Severe hepatic impairment
5. Evidence of infection at or near the proposed needle insertion site
6. Any sensorimotor deficit, whether acute or chronic, as determined by the PI
7. Chronic use of opioid medication
8. BMI  $\geq 35$

### Methods:

#### Research related procedure: Planned statistical analyses

All analyses for this pilot study will be conducted in JMP Pro 12.0 (SAS Institute, Cary, NC). Categorical measures (e.g. block success) will be summarized as percentages (%). For continuous measures (e.g. pain scores), normally distributed measures will be summarized as means and standard deviations, and non-normally distributed measures will be summarized as median with interquartile range. Differences in block success will be examined with  $\chi^2$  tests. Differences in continuous measures will be examined through t-tests, with transformation of outcomes as necessary to satisfy assumptions of the statistical test.  $P < 0.05$  will be considered statistically significant.

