#### Sample size justification

This is a pilot study proposing the assessment of a convenience sample of  $n=30$ . We calculated the precision in estimation of the incidence of block failure is 10, 15, or 20%, assuming power of 80%. An additional six subjects (for a total of 36) will be enrolled in the event that subjects discontinue participation in the study before completing all study interventions/interactions (either due to adverse event, withdrawal, etc.). The respective width of the 95% CIs for these estimates would be 0.25, 0.28, 0.31.

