#### Peripheral nerve blocks

Standard of care: At the Malcom Randall VA, peripheral nerve blocks and general anesthesia are usually administered. The choice of nerve blocks is usually left up to the

Protocol #201702402

IRB version: 03.09.04

PI version: 03/26/2025

anesthesiologist's preference. A time out procedure will be performed confirming the patient's identity and the proposed surgical procedure. The various block sites will be cleansed with Chlorohexidine prep solution. Femoral and sciatic nerve continuous nerve catheters are the most commonly performed blocks for patients receiving lower extremity amputation.

Research related procedure: After administration of intravenous sedation, lateral femoral cutaneous and obturator nerve blocks (in addition to the femoral and sciatic catheters) will be performed under ultrasound guidance.

All enrollees will have ultrasound-guided femoral and sciatic nerve blocks placed per current practice at the VA. Single-injection obturator and lateral femoral cutaneous nerve blocks will also be performed.

All nerve blocks will be performed by [name], who has expertise in ultrasound-guided regional anesthesia. Block time will be counted as the time from needle insertion until the completion of the injections. Any inadequate/failed blocks will be recorded.

Inadequate blocks will have analgesic supplementation conversion to general anesthesia. After surgery, pain scores and side effects will be recorded until discharge from the recovery room. The total dose of ropivacaine will be under 300mg or 3-4 mg/kg.

[figure not shown]
Research related procedure: Block onset characteristics and incidence of adverse events will be recorded.

Standard of care: The Veteran will then be transported to the operating room.

Research related procedure: Intravenous sedation using propofol or dexmedetomidine will be administered. General anesthetic agents, opioids, and multimodal analgesics will be initially avoided so as to not mask an inadequate block. The administration of these agents, as well as conversion to general anesthesia or surgical local anesthetic supplementation, will be recorded. The incidence of block- and procedure-related adverse events will be recorded.

Standard of care: After surgery, all patients will be transported to the post anesthesia care unit (PACU). The patients will then be discharged to a ward or ICU bed as indicated.

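### Chi-square tests of block success are planned with nothing to compare against, and the 95% confidence interval that justifies n=30 is not in the analysis plan

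*Combined protocol and SAP*

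**What the plan says.** Four parts of the combined protocol and SAP bear on this.

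- **Section 5, Specific Aims.** The primary endpoint is binary for each patient: surgery completed under sedation alone, or not. The section then adds: "Instances of intraoperative analgesic administration or conversion to general anesthesia will be compared". It does not say with what.
- **Section 6, Planned statistical analyses.** "Categorical measures (e.g. block success) will be summarized as percentages". The next step is inferential: "Differences in block success will be examined with" chi-square tests. For the rest, "Differences in continuous measures will be examined through t-tests, with transformation of outcomes as necessary to satisfy assumptions of the statistical test". The significance level is 0.05. No groups, time points or reference values are given, and no confidence interval is mentioned.
- **Section 6, Sample size justification.** The basis for n=30 is estimation: "We calculated the precision in estimation of the incidence of block failure", for assumed rates of 10%, 15% and 20%. The precision claimed for them is then given: "The respective width of the 95% CIs for these estimates would be 0.25, 0.28, 0.31".
- **Section 6, Peripheral nerve blocks.** Two of the four blocks are assigned here: "All enrollees will have ultrasound-guided femoral and sciatic nerve blocks placed per current practice at the VA". The text then turns to the remaining two nerves: "Single-injection obturator and lateral femoral cutaneous nerve blocks will also be performed". No patient group is described as going without any of the four.

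**The concern.** A test of differences needs two or more groups, repeated measurements, or a fixed reference value. The design supplies one group of patients treated alike, and the analysis section supplies none of the other ingredients. The sample-size section, by contrast, treats the study as estimation of a single proportion. The two sections therefore describe different analyses, and the one that fits the design is missing from the analysis plan.

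Two things are at stake. The main result could be published as a percentage with no statement of how uncertain it is, although the pilot is meant to show feasibility and guide a larger study. And because the comparison is unnamed, it could be chosen once the data are known (amputation against disarticulation, one sedative against the other, nerve against nerve), in which case P<0.05 would lose its usual meaning. The text does not show that anyone intends this. It leaves it open.

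**Working it through.** **Inputs.** n=30 evaluable; assumed failure rates p = 0.10, 0.15, 0.20; stated 95% interval widths 0.25, 0.28, 0.31 (all from Sample size justification). Significance level 0.05 (Planned statistical analyses). z = 1.96, z² = 3.8415.

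**1. Reproducing the plan's widths.** The Wilson interval with continuity correction has limits

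- L = [2np + z² − 1 − z√(z² − 2 − 1/n + 4p(n(1−p) + 1))] / [2(n + z²)]
- U = [2np + z² + 1 + z√(z² + 2 − 1/n + 4p(n(1−p) − 1))] / [2(n + z²)]

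For p = 0.10:

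- L = (8.8415 − 1.96 × √13.008) / 67.683 = 0.026
- U = (10.8415 + 1.96 × √16.208) / 67.683 = 0.277
- width = 0.251

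Widths for all three rates, with other common methods for comparison:

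| Method (n=30) | 10% | 15% | 20% |
|---|---|---|---|
| Stated in the plan | 0.25 | 0.28 | 0.31 |
| Wilson, continuity-corrected | 0.251 | 0.283 | 0.307 |
| Clopper-Pearson | 0.244 | 0.281 | 0.309 |
| Wilson | 0.222 | 0.253 | 0.278 |
| Wald, 2z√(p(1−p)/n) | 0.215 | 0.256 | 0.286 |

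(15% of 30 is 4.5 patients, so the Clopper-Pearson entry there is interpolated.) The stated widths are sound and come from a one-sample interval at n=30. The method matters: at 20% the width runs from 0.278 to 0.309.

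**2. What a bare percentage leaves out.** Exact limits for x failures in 30 are the 2.5% quantile of Beta(x, 31−x) and the 97.5% quantile of Beta(x+1, 30−x).

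- 3/30 = 10.0%: 2.1% to 26.5%
- 6/30 = 20.0%: 7.7% to 38.6%

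**3. Can the chi-square be read as one-sample?** It would need a reference rate p₀. The only external rate quoted for this operation by itself is the 5.6% in Background, which is 30-day mortality. The 10%, 15% and 20% are precision scenarios, not null values. They are borrowed here only to show how far the answer depends on the missing value. With 7 failures, X² = (7 − 30p₀)² / [30p₀(1−p₀)]:

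- p₀ = 0.10: (7 − 3)² / 2.7 = 5.93, P = 0.015
- p₀ = 0.15: (7 − 4.5)² / 3.825 = 1.63, P = 0.20
- p₀ = 0.20: (7 − 6)² / 4.8 = 0.21, P = 0.65

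Expected failures are small at the lower rates. The exact binomial P against 10% is 0.026, which is on the same side of 0.05.

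**4. Can it be read as a contrast between the four nerves?** The plan does not say so, and that would not address the patient-level primary endpoint. The four results would also be paired within patients. In 20,000 simulated trials of 30 patients and four nerves, with equal failure rates of 10% to 20%, the ordinary chi-square rejected in 3.9% to 4.6% of trials at zero within-patient correlation but only 1.2% to 1.5% at a latent correlation of 0.5. Cochran's Q stayed at 3.0% to 4.8% across correlations of 0 to 0.8. The correlations are assumptions, since the documents give none. This step bears only on the optional advice about paired methods.

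**The case against.** The best defence is that this is a feasibility pilot on a convenience sample, for which description is a legitimate primary analysis, and the plan does specify a percentage. The sample-size subsection directly follows the analysis subsection and names the quantity, the 95% level and the expected widths, so reporting the interval is the natural reading. Any reader given the counts could rebuild it. The tests are also not necessarily meaningless: patients can differ by procedure or sedative, and each has four nerves blocked, so contrasts exist in the data. A neutral remedy would be to name the comparison or delete the test.

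Much of this is fair. The percentage is valid, the interval may well be intended, and nothing shows a plan to choose comparisons after the fact. But a plan that stopped at description would not set significance tests and a threshold, and this one does. None of the possible contrasts is named, and none answers the primary question, which concerns one proportion in one group. An interval used to size the study should be listed among its outputs with its method, because the methods differ visibly at n=30.

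**Conclusion.** The concern holds. The only inference written for the primary endpoint is a test that the documented design cannot support, and the one-sample 95% interval on which n=30 rests is not a planned output. No figure in the plan is wrong: the stated widths reproduce. The cost is unreported uncertainty of roughly 24 to 31 percentage points in full exact width (3 and 6 failures in 30), and a possible P value whose comparison is undefined. The conclusion assumes a single-group design. The documents never use that term, but all enrollees receive the same blocks and no other group is described. It should be fixed before analysis. It does not affect patients, data collection or sample size.

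**What to change.** In Planned statistical analyses:

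- State that the primary analysis is the proportion of patients who achieve (or fail) surgical anesthesia as defined in Specific Aims, with a two-sided 95% confidence interval by a named method. Clopper-Pearson would serve, as would the continuity-corrected Wilson interval that reproduces the stated widths.
- Delete the chi-square test for block success.
- Delete the t-tests unless their groups or time points are named. The provision for transforming outcomes deals with distribution, not with the missing comparison.
- If contrasts between nerves are wanted, name them, label them exploratory and use a paired method (Cochran's Q, with McNemar for pairs).

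In Specific Aims, say that instances of analgesic use or conversion will be summarised rather than compared.

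The cost is a few sentences of wording. The study gives up P<0.05 claims that its design could not have supported.

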#### Sample size justification

This is a pilot study proposing the assessment of a convenience sample of  $n=30$ . We calculated the precision in estimation of the incidence of block failure is 10, 15, or 20%, assuming power of 80%. An additional six subjects (for a total of 36) will be enrolled in the event that subjects discontinue participation in the study before completing all study interventions/interactions (either due to adverse event, withdrawal, etc.). The respective width of the 95% CIs for these estimates would be 0.25, 0.28, 0.31.

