Research related procedure: Numerical rating scale pain scores (0-10) will be obtained upon arrival and recorded hourly until PACU discharge. Nausea, pruritis, and other side

effects will be recorded. Patients will be called or visited 24-48 hours post procedure to inquire about patient satisfaction. The medical record will be subsequently reviewed to assess 30-day mortality and again at the conclusion of subject enrollment. The planned maximum duration of study participation will be approximately 48 hours from the date of surgery. Additionally, data on survival beyond this point may be obtained from administrative sources (CPRS) to assess 30-day and long-term mortality.

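### Does the six-patient allowance for discontinuations leave the block failure rate without a usable denominator?

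*Combined protocol and SAP*

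**What the plan says.** The Sample size justification begins: "This is a pilot study proposing the assessment of a convenience sample of" 30. Six more may be enrolled, for a total of 36, "in the event that subjects discontinue participation in the study before completing all study interventions/interactions (either due to adverse event, withdrawal, etc". For assumed block failure of 10, 15 or 20% it then says: "The respective width of the 95% CIs for these estimates would be 0.25, 0.28, 0.31".

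The Specific Aims set the primary outcome: "Surgical anesthesia will be defined as the performance of surgery using only sedative medications (propofol or dexmedetomidine"), with no opioid or other analgesic, no infiltration of local anesthetic and no change to general anesthesia. The Planned statistical analyses paragraph says: "Categorical measures (e.g. block success) will be summarized as percentages". It names no analysis set.

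The Peripheral nerve blocks section covers data collection. "Any inadequate/failed blocks will be recorded". Supplementary agents, conversions and adverse events are also recorded. Two items come after surgery: "Patients will be called or visited 24-48 hours post procedure to inquire about patient satisfaction", and "The medical record will be subsequently reviewed to assess 30-day mortality".

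**The concern.** The failure rate is the pilot's main result and is meant to guide later studies. Three features together look awkward.

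- Adverse events are a named reason for discontinuing, and a patient who stops because of a block-related event bears directly on feasibility.
- Completion runs to the 24-48 hour contact, while the primary outcome is settled when surgery ends. A patient who misses only the satisfaction call would count as discontinued although the block outcome is known.
- No section says whether the denominator is 30, 36, all patients with a block started, or completers.

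If the six extra patients simply replaced those who stopped, and the latter were dropped, the failure and adverse-event rates could be biased, most plausibly downward if stopping follows block trouble. The denominator for 30-day mortality is not stated either, though it is less exposed because it comes from record review.

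**Working it through.** **1. Which n the stated widths rest on.** Inputs from the Sample size justification: n = 30; p = 0.10, 0.15, 0.20; 95% confidence, taken as two-sided. The continuity-corrected Wilson interval, with q = 1 − p and z = 1.96, is

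- lower = [2np + z² − 1 − z√(z² − 2 − 1/n + 4p(nq + 1))] / [2(n + z²)]
- upper = [2np + z² + 1 + z√(z² + 2 − 1/n + 4p(nq − 1))] / [2(n + z²)]

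At n = 30, p = 0.10:

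- lower = (8.8415 − 1.96 × √13.008) / 67.683 = 0.026
- upper = (10.8415 + 1.96 × √16.208) / 67.683 = 0.277
- width = 0.2506

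| Width at p = | 0.10 | 0.15 | 0.20 |
|---|---|---|---|
| Stated | 0.25 | 0.28 | 0.31 |
| n = 30 | 0.2506 | 0.2825 | 0.3073 |
| n = 36 | 0.2263 | 0.2566 | 0.2800 |

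Clopper-Pearson at n = 30 gives 0.244, 0.281, 0.309, with only the first off by 0.01. The precision was therefore planned on 30. The total of 36 is the usual attrition inflation: 30 / (1 − 6/36) = 36. Neither figure says who is analysed.

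**2. Which patients lack an outcome.** Setting the Specific Aims definition against what the Peripheral nerve blocks section records:

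| Course | Primary outcome |
|---|---|
| Leaves before any block | Not part of a block failure rate; the plainest use of the allowance |
| Surgery under sedation alone, later contact missed | Success, known at end of surgery |
| Surgery with analgesic, infiltration or conversion | Non-success by definition, recorded |
| Blocks abandoned, surgery by another technique | Definition not met, so non-success; failed block recorded |
| Block started but no surgery, or data withdrawn | None; no rule written |

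Only the last row is undetermined.

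**3. How far the rate could move.** The documents give no discontinuation data, so the counts here are assumed. With f failures among m completers and k patients who stop after a block is started, the rate among all block-started patients lies between f/(m + k) and (f + k)/(m + k).

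| Completers | Exact 95% CI | k | Lowest | Highest |
|---|---|---|---|---|
| 3/30 = 10.0% | 2.1–26.5% | 2 | 3/32 = 9.4% | 5/32 = 15.6% |
| 3/30 = 10.0% | 2.1–26.5% | 6 | 3/36 = 8.3% | 9/36 = 25.0% |
| 6/30 = 20.0% | 7.7–38.6% | 6 | 6/36 = 16.7% | 12/36 = 33.3% |

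Every range sits inside the Clopper-Pearson interval for the completer result. The highest values with k = 6 need all six extra patients to be enrolled, all six discontinuations to come after a block is started, and all six to count as failures.

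**The case for a change.** The strongest case for a change is that the counting rule can be fixed beforehand at almost no cost. It would also settle a question that reaches the main result: the shift from 10% to between 15.6% and 25.0% covers most of the 10-20% range the plan itself considered, and goes beyond it. A shift inside the sampling interval is still a systematic one, and pilot status is no excuse when the estimate is meant to inform larger studies.

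Part of this stands. The denominator is unwritten, and a patient with a block started but no operation has no stated classification. The rest is weaker. Nothing says that discontinued patients are excluded, and planning on 30 with an allowance is ordinary practice. Dropping a patient with a known block outcome for a missed satisfaction call would need a second assumption on top of the first. The direction of bias is also not established: several of the risks listed under Possible Discomforts and Risks, such as hematoma, paresthesia or infection, are not block failures under the Specific Aims. Nor does anything suggest that adverse events in patients who stop would be discarded.

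**Conclusion.** The concern identifies missing detail, not an error. No rule in the plan yields a wrong failure rate. The Specific Aims definition and the recorded failed blocks and conversions classify every patient who is operated on after a block is started, whatever happens afterwards. A competent analyst would use those patients as the denominator. Anyone with a block started but no surgery, or with data withdrawn, would be listed separately with reasons, and the planned record review would serve for mortality.

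The residual uncertainty is confined to that last small group. At the assumed extreme of six such patients beside 3/30, it spans 8.3% to 25.0%, within the 2.1% to 26.5% that sampling error alone allows; with two it spans 9.4% to 15.6%. This conclusion rests on discontinued patients with a known intraoperative outcome being kept, which the text permits and nothing in it contradicts. No change to the plan is needed.
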